9.4 STATISTICAL ANALYSES

9.4.1 GENERAL APPROACH

This protocol provides a summary of the statistical analyses, and the SAP provides additional details.

- Descriptive statistics will be reported by study arm. Categorical data will be presented as percentages, and continuous data will be summarized as means and standard deviations.
- Buprenorphine access will be compared between arms by fitting a logistic regression model. Specification of the model is available in the SAP.

- Cumulative days of buprenorphine will be compared between arms by fitting a linear regression model. Specification of the model is available in the SAP.
- Depression symptom severity and PTSD symptom severity will be analyzed using non-response weighted linear regression models. Additional model details and specification of covariates are provided in the SAP.

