9.4.2 ANALYSIS OF THE PRIMARY ENDPOINT(S)

This protocol provides a summary of the statistical analyses, and the SAP provides additional details.

- Buprenorphine access is a time-to-event outcome and will be compared between arms by fitting a Cox proportional hazard regression model. Specification of the model is available in the SAP.
- Days of cumulative buprenorphine treatment will be compared between arms by fitting a linear regression model. Specification of the model is available in the SAP.
- Depression symptom severity and PTSD symptom severity are ordinal scales and will be analyzed using non-response weighted linear regression models. Additional model details and specification of covariates are provided in the SAP.

The primary analyses will be performed for the intention-to-treat population, which consists of all randomized subjects. Procedures for handling missing data are provided in the SAP.

A union-intersection test will be used to test the overall success of the study that combines the four primary outcomes into a single composite hypothesis. In particular, the null hypothesis is the intersection of the four primary outcome null hypotheses (i.e., all null hypotheses are true), and the alternative is the union of the alternative hypotheses (i.e., at least one alternative hypothesis is true). A Bonferroni or Benjamini-Hochberg correction on the individual hypotheses will be used to control the error rate of this composite test. The four primary hypotheses will be analyzed with a Type I error of 1.25%, which accounts for the multiple primary outcomes using a Bonferroni correction to control the family-wise error rate at 5% ($0.05/4 = 0.0125$).

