2.5 Definitions of outcomes

2.5.1 Primary outcomes

Table 1 defines the primary outcomes of this study. The hypotheses associated with these outcomes are as follows:

1. We hypothesize that patients with a new OUD episode of care who are randomized to CC-COD/CC-COD+ will receive buprenorphine within fewer days after that care episode

than new OUD patients who are randomized to enhanced usual care. Alternatively, the null hypothesis is that there will be no difference in the number of days until receipt of buprenorphine with a new OUD episode of care.

2. We hypothesize that patients who are randomized to CC-COD/CC-COD+ will have more days of buprenorphine treatment within 180 days of study enrollment than patients who are randomized to enhanced usual care. Alternatively, the null hypothesis is that there will be no difference in the number of days of cumulative buprenorphine treatment within 180 days of study enrollment.
3. We hypothesize that, among patients with probable depression at study enrollment, those who are randomized to CC-COD/CC-COD+ will have a greater reduction in depression symptoms 6 months after study enrollment compared to those who are randomized to enhanced usual care. Alternatively, the null hypothesis is that there will be no difference in depression symptoms 6 months after study enrollment among those with probable depression at enrollment.
4. We hypothesize that, among patients with probable PTSD at study enrollment, those who are randomized to CC-COD/CC-COD+ will have a greater reduction in PTSD symptoms 6 months after study enrollment compared to those who are randomized to enhanced usual care. Alternatively, the null hypothesis is that there will be no difference in PTSD symptoms 6 months after study enrollment among those with probable PTSD at enrollment.

A union-intersection test will be used to test the overall success of the study that combines the four primary outcomes into a single composite hypothesis. In particular, the null hypothesis is the intersection of the four primary outcome null hypotheses (i.e., all null hypotheses are true), and the alternative is the union of the alternative hypotheses (i.e., at least one alternative hypothesis is true). As described in subsequent sections, either a Bonferroni or Benjamini-Hochberg correction on the individual hypotheses will be used to control the error rate of this composite test.

Table 1: Definition of primary outcomes

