Outcome	Population ^a	Definition	Measure Scale	Source
Buprenorphine access	Study participants with a new episode of OUD care (no care for at least 30 days prior)	Number of days until first buprenorphine prescription after study enrollment	Time-to-event	Survey, PMP
Buprenorphine continuity of care	Study participants not on methadone at baseline	The cumulative number of days the patient receives buprenorphine during the 180 days after study enrollment.	Continuous	Survey, PMP
MDD symptom severity	Study participants with probable MDD at baseline (PHQ-8 \geq 10)	PHQ-9 at 6 months	Sum of items (0-27)	Survey
PTSD symptom severity	Study participants with probable PTSD at baseline (PC-PTSD-5 \geq 3)	PCL-5 at 6 months	Sum of items (0-80)	Survey

^a Study participants means all study participants who consented and were randomized to the intervention or to EUC.

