3.3 Baseline Characteristics

We will conduct descriptive analyses comparing CC-COD/CC-COD+ and EUC characteristics at baseline using a Chi-squared test for categorical variables and a two sample t-test otherwise. Table 6 provides the demographic characteristics of the study participants at baseline. Table 7 provides all outcomes at baseline and at the 6-month follow-up.

Table 6: Sociodemographics and other covariates at baseline

	Overall	Treatment Assignment	
		CC-COD	EUC
Age, n (%)			
18-30 years			
31-40 years			
41-50 years			
51 years and older			
Sex, n (%)			
Male			
Female			
Gender-neutral sex designation (X)			
Race/Ethnicity, n (%)			
White, Non-Hispanic			
Hispanic			
Other race, Non-Hispanic			
Education, n (%)			
Less than high school diploma			
High school graduate/GED			
Any college/higher-level education			
Marital Status, n (%)			
Never Married			
Married/Partnered			
Divorced/Separated/Widowed			
Prior MOUD, n (%)			
Health system, n (%)			
Health system 1			
...			
Health system 4			

Table 7: Outcomes at baseline and 6-months

	Baseline			6-Months		
	Overall	CC-COD	EUC	Overall	CC-COD	EUC
Primary outcomes						
Buprenorphine access, mean (SD) ¹						
Buprenorphine continuity of care, mean (SD)						
PTSD, n (%)						
PTSD Symptoms, mean (SD)						
MDD, n (%)						
MDD Symptoms, mean (SD)						
Secondary outcomes						
Access to MDD and/or PTSD treatment, n (%)						
Quality of care for MDD, n (%)						
Quality of care for PTSD, n (%)						
MDD remission, n (%)						
MDD response, n (%)						
PTSD remission, n (%)						
PTSD response, n (%)						
Suicidality, n (%)						
Opioid Use Frequency, mean (SD)						
Opioid Overdose Events, n (%)						
Physical Health Functioning, mean (SD)						
Mental Health Functioning, mean (SD)						
Exploratory outcomes						
Drug use frequency, mean (SD)						
Stimulant use frequency, mean (SD)						
Alcohol use, mean (SD)						
Opioid Overdose Risk Behaviors, mean (SD)						
Opioid use severity, mean (SD)						

NOTES: ¹Gray cells indicate outcomes not measured at baseline

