3.4.5 Survival outcome

Buprenorphine access, the survival outcome that is measured in the PMP and survey will be analyzed using a Cox proportional hazard regression model including health-system, prior MOUD exposure, and treatment assignment as predictors. The Cox proportional regression model is given by:

$$h(t) = h_0(t) * \exp(\alpha_j + \nu P_{ij} + \beta T_{ij})$$

where α_j are health system-level fixed effects, and e^β is the hazard ratio effect of CC-COD over EUC. The statistical hypotheses from the Cox proportional hazard regression will be of the form:

$$H_0: \beta = 0 \text{ vs}$$
$$H_1: \beta \neq 0.$$

Outcomes that are measured as part of the 6-month follow-up survey may be weighted to account for nonresponse as previously described. Again, if we do not have sufficient sample size to support modeling P_{ij} (prior MOUD treatment), then it will be removed from a given model. We will assess this for each continuous outcome by examining if we have at least 30 individuals with and without prior MOUD treatment in our analytic sample. We will right censor all observations for those individuals who did not ever receive buprenorphine during the course of follow-up for these analyses.

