3.5 Primary outcome results

Table 11: Estimated effect of CC-COD over EUC for primary outcomes, including descriptive statistics by treatment arm. Descriptive statistics include counts and percentages for binary outcomes and means and standard deviations for all others.

Outcome	CC-COD	EUC	Effect Estimate ¹
Buprenorphine Access			
Buprenorphine Continuity of Care			

MDD Symptoms			
PTSD Symptoms			

NOTE: ¹ The effect estimate for all outcomes is reported as the difference between CC-COD and EUC from models that include fixed effects for clinic, prior MOUD exposure, and treatment assignment. Binary outcomes are modeled using logistic regression and converted to a marginal risk difference using recycled predictions.

References

3. Buuren Sv, Groothuis-Oudshoorn K. mice: Multivariate imputation by chained equations in R. *Journal of Statistical Software.* 2010;1-68. doi: doi: 10.1111/j.0006-341X.1999.00652.x.
5. [name] BA, Schuler MS, Cefalu M, Ayer L, Godley M, Greifer N, Coffman DL, McCaffrey DF. A Tutorial for Propensity Score Weighting for Moderation Analysis With Categorical Variables: An Application Examining Smoking Disparities Among Sexual Minority Adults. *Med Care.* 2023;61(12):836-45. Epub 20231002. doi: 10.1097/mlr.0000000000001922. PubMed PMID: 37782463; PMCID: PMC10840831.

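### Buprenorphine access is a censored Cox endpoint, but the SAP result tables report it as mean (SD) and a difference, and Protocol 9.4.1 still names logistic regression

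*Protocol*

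**What the plan says.** **Model.** In Protocol 9.4.1, "Buprenorphine access will be compared between arms by fitting a logistic regression model". In Protocol 9.4.2, "Buprenorphine access is a time-to-event outcome and will be compared between arms by fitting a Cox proportional hazard regression model". Protocol 8.1 explains that access was deliberately changed from a binary to a time-to-event measure. SAP Table 1 gives its scale as time-to-event. SAP 3.4.5 fits a Cox model in which the exponentiated treatment coefficient "is the hazard ratio effect of CC-COD over EUC", and adds: "We will right censor all observations for those individuals who did not ever receive buprenorphine during the course of follow-up for these analyses".

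**Reporting.** The Table 11 note (SAP, Primary outcome results) says: "The effect estimate for all outcomes is reported as the difference between CC-COD and EUC". The Table 11 caption allows counts and percentages for binary outcomes and means with standard deviations for everything else. The only conversion rule in the note is for binary outcomes. In SAP Table 7 (section 3.3) the row label begins "Buprenorphine access, mean (SD".

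**Time origin.** Hypothesis 1 in SAP 2.5.1 says that intervention patients "will receive buprenorphine within fewer days after that care episode" than controls. Protocol 9.1 words it in the same way and refers to the point at which the episode begins. SAP Table 1 defines the endpoint as "Number of days until first buprenorphine prescription after study enrollment", and the revised definitions in Protocol sections 3 and 8.1 do likewise.

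**The concern.** Access is one of four primary endpoints, each tested at 0.0125. Its result has to come from a model that handles participants who never start buprenorphine, and has to be presented on that model's scale.

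The table shells do not allow this. A censored participant has no observed number of days to first prescription. To fill a mean (SD) cell, an analyst must either drop that participant or enter the censoring time as if it were a start. Dropping compares groups selected by something that happened after randomisation. If the intervention led more people to start without changing how quickly starters start, the mean days would be equal in both arms although the hazard ratio favoured the intervention. Entering censoring times yields a mean that depends on the length of follow-up.

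The stray logistic bullet and the two descriptions of time zero add avoidable ambiguity to a primary endpoint.

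**Working it through.** **1. Which model.** Protocol 9.4.1 says logistic, gives no time window, and refers to the SAP for the specification. Protocol 9.4.2, Protocol 8.1, SAP Table 1 and SAP 3.4.5 all say time-to-event or Cox. The SAP's logistic model (3.4.3) is for binary outcomes, and Table 1 does not class access as binary. The Schedule of Activities also still shows the old measure (prescription within 30 days of diagnosis, from the health record), which supports reading the 9.4.1 bullet as a remnant.

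**2. Whether the tables fit the model.** SAP 3.4.5 produces a hazard ratio, a number of starters and a number censored. Table 11 offers a descriptive cell per arm (mean and SD) and a difference. Table 7 offers mean (SD). Neither has a place for a hazard ratio, a count of starters or censored participants, or a Kaplan-Meier estimate.

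**3. Time zero.** The hypotheses count from the care episode; the revised endpoint definitions count from enrollment. Protocol 9.3 restricts the population to participants whose episode is new at enrollment, defined by no visit with an OUD diagnosis in the preceding 30 days. That points to the same origin, although no sentence says that the episode starts on the enrollment date.

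**4. How many participants have no start time.**

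Inputs: alpha 0.05/4 = 0.0125, which reproduces the stated value; two-sided tests (SAP 3.4.2); 80% power (SAP 3.5); 1:1 allocation (SAP 2.7); N = 137, detectable hazard ratio 0.45 or 2.25 reversed, mean 26.0 and SD 31.9 days (SAP 3.5.1). The number of starters is not given, so the detectable hazard ratio cannot be reproduced from stated inputs. The step below solves backwards for the number of starters.

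Schoenfeld: events = 4 × (z for 0.00625 + z for 0.20)² / (ln HR)², with 2.498 + 0.842 = 3.339 after rounding.

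- HR 2.25: 4 × 3.339² / 0.811² = 67.8, so 68 events; 68/137 = 49.6%.
- HR 0.45: 4 × 3.339² / 0.799² = 70.0, so 70 events; 70/137 = 51.1%.
- The two differ because 1/0.45 = 2.22, not 2.25.
- Freedman's formula gives 76 and 78 events (55% and 57%).
- If all 137 had started, the detectable hazard ratio would be exp(−3.339/√(137/4)) = 0.565, not 0.45.

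On these formulas, between 59 (137 − 78) and 69 (137 − 68) participants have no start time.

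**5. Cross-check with the printed mean.** If 67 of 137 were censored at day 180, the mean observed time would be at least 67 × 180/137 = 88 days, even if every starter began on day 0. A mean of 26.0 days could then describe starters only.

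**6. What a starters-only mean would show.** In a simulation with assumed inputs (N = 137, exponential times, 51% starting by day 180, true hazard ratio 2.22, alpha 0.0125), the Cox test had 79% power. A t-test of days among starters had 3.5%, with a mean difference of −8.4 days. The starters-only figure stays about as low when starts are concentrated early. The exact values depend on the assumptions. The contrast arises because the starters-only mean discards the information on who starts.

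**The case against.** Much of the case on the other side stands.

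- **The model is not open.** Protocol 9.1 says that the SAP holds all statistical considerations, and for this endpoint the SAP specifies only Cox. A reader might infer two rival primary analyses that could fall on different sides of 0.0125. The documents do not support that: the logistic bullet has no time window and cannot be run as written. Nor is the cost of a wrong choice well determined. In the simulation above, logistic regression at 180 days had 77% power against 79% for Cox. At 30 days it had 9%, but that set-up implies a starter mean near 78 days. With early-concentrated times that match a mean of 25 to 27 days, the 30-day figure is about 60%.
- **The time origin is mostly wording.** A reader might infer a bias from counting days from an episode that begins after randomisation and that the intervention can bring forward. Protocol 9.3 places the new episode at enrollment, and every revised definition counts from enrollment, so no such bias is shown.
- **The primary test keeps never-starters.** A reader might infer that half the sample is dropped from the primary analysis. SAP 3.4.5 censors these participants and does not exclude them. Table 7 is descriptive and has no effect column. The Table 11 note is generic, and also names clinic effects where SAP 3.4.5 uses health systems.
- **The count of starters is back-solved** from rounded figures. The SAP does not state its final power method, and its revision history mentions simulation.

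What remains is the Table 11 rule. It covers all outcomes, makes no exception for the time-to-event one, and together with Table 7 prescribes a display that the Cox analysis cannot fill.

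**Conclusion.** The point holds as an error in the text that should be corrected. It does not show that the primary analysis is undetermined or biased.

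Certain from the documents: Protocol 9.4.1 contradicts 9.4.2, 8.1 and the SAP; and Tables 7 and 11 prescribe mean (SD) and, in Table 11, a difference for an outcome whose effect the SAP defines as a hazard ratio with censoring. The wording of time zero in hypothesis 1 should be aligned with the endpoint definition.

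The size is an assumption. With a Schoenfeld-type calculation behind the stated detectable effect, about 68 to 70 of 137 participants started and roughly half would have no value to enter in a mean. If the SAP's figure came from another method, the share differs. The reporting rule is unsuitable for any appreciable amount of censoring.

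**What to change.** - **Protocol 9.4.1:** replace the logistic bullet for access with the Cox model of 9.4.2.
- **Protocol 9.1 and SAP 2.5.1, hypothesis 1:** name study enrollment as time zero.
- **SAP Table 11:** for access, report the hazard ratio (CC-COD/CC-COD+ over EUC) with its confidence interval, and exempt this outcome from the difference rule in the note. State that values above 1 mean faster access, because SAP 3.5.1 attaches 0.45 to fewer days, the reverse of the direction in 3.4.5.
- **SAP Tables 7 and 11:** replace mean (SD) for access with the number starting and the number censored by arm, plus a summary that respects censoring, such as a Kaplan-Meier estimate.

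The cost is wording and table shells. No new data, endpoint change or sample size change is needed.

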9.4.2 ANALYSIS OF THE PRIMARY ENDPOINT(S)

This protocol provides a summary of the statistical analyses, and the SAP provides additional details.

- Buprenorphine access is a time-to-event outcome and will be compared between arms by fitting a Cox proportional hazard regression model. Specification of the model is available in the SAP.
- Days of cumulative buprenorphine treatment will be compared between arms by fitting a linear regression model. Specification of the model is available in the SAP.
- Depression symptom severity and PTSD symptom severity are ordinal scales and will be analyzed using non-response weighted linear regression models. Additional model details and specification of covariates are provided in the SAP.

The primary analyses will be performed for the intention-to-treat population, which consists of all randomized subjects. Procedures for handling missing data are provided in the SAP.

A union-intersection test will be used to test the overall success of the study that combines the four primary outcomes into a single composite hypothesis. In particular, the null hypothesis is the intersection of the four primary outcome null hypotheses (i.e., all null hypotheses are true), and the alternative is the union of the alternative hypotheses (i.e., at least one alternative hypothesis is true). A Bonferroni or Benjamini-Hochberg correction on the individual hypotheses will be used to control the error rate of this composite test. The four primary hypotheses will be analyzed with a Type I error of 1.25%, which accounts for the multiple primary outcomes using a Bonferroni correction to control the family-wise error rate at 5% ($0.05/4 = 0.0125$).

9.4.3 ANALYSIS OF THE SECONDARY ENDPOINT(S)

Secondary endpoints will be grouped into domains of conceptually related endpoints, and each will be analyzed adjusting for multiple comparison within domain. Preliminary domains are as follows:

Mental Health

- Access to MDD and/or PTSD treatment
- Quality of care for MDD

- Quality of care for PTSD
- MDD remission
- MDD response
- PTSD remission
- PTSD response
- Active suicidal ideation

Substance Use

- Opioid use frequency
- Opioid overdose events

Overall Health

- Physical health functioning
- Mental health functioning

Secondary endpoints will be analyzed using similar approaches as described for the primary endpoints. Additional model details are provided in the SAP. Other statistical issues, e.g. loss to follow up and missing data, will be accounted for using the same techniques as with the primary outcomes.

9.4.4 BASELINE DESCRIPTIVE STATISTICS

Baseline descriptive statistics will be reported by study arm. Categorical data will be presented as percentages, and continuous data will be summarized as means and standard deviations. Two-sample comparisons of study arms will be reported using appropriate statistical tests (e.g. two sample t-tests and chi-squared tests). The SAP provides additional details and a list of baseline characteristics to be summarized.

Baseline Descriptive Statistics for CR:

The CR will use the same baseline descriptive statistics as the primary study.

9.4.5 SUB-GROUP ANALYSES

Analyses of moderators of the effectiveness of CC-COD on study outcomes will be conducted. The sub-groups of interest for these analyses are documented in Section 3. Similar models to those for the primary and secondary analyses will be used, but the models will include the necessary interaction between the randomization assignment and the sub-group. The SAP provides additional details.

Sub-Group Analyses for CR:

N/A

9.4.6 EXPLORATORY ANALYSES

All planned exploratory analyses will be described in the SAP.

10 SUPPORTING DOCUMENTATION AND OPERATIONAL CONSIDERATIONS

10.1 REGULATORY, ETHICAL, AND STUDY OVERSIGHT CONSIDERATIONS

10.1.1 INFORMED CONSENT PROCESS

10.1.1.1 CONSENT/ASSENT AND OTHER INFORMATIONAL DOCUMENTS PROVIDED TO PARTICIPANTS

The consent form used in this study complies with all required regulatory elements. The consent form describes in detail the study intervention, study procedures and the risks involved. The participant will need to give explicit permission prior to participating in the study. This permission will be documented in the data collection form and a copy of the informed consent form will be given to every participant for their records. The informed consent will be available in English and Spanish. The correct form will be selected based on the participant's preference and status of language proficiency. A copy of both consent forms is included with this protocol.

Because SPs will not be participating in any research activities, they will not be enrolled and consented in the CR trial. As part of the consent process for participation in the CR, participants will be told that if they are randomized to CC-COD+, the care coordinator will ask if they have an SP who might be willing to meet with the care coordinator to learn about ways to support the participants recovery. However having an SP is not an inclusion criterion.

